
5. There is a major gap in our understanding of the genetic factors that determine response to OXY in all ethnic groups including under-represented populations. In contrast to the multiple GWAS studies identifying genetic risk factors for hyperuricemia and gout, there has been no published GWAS related to ALLO response. In preliminary studies using samples from individuals of European ancestry, we conducted the first GWAS of response to ALLO. We attempt to fill this gap by evaluating the effects of ABCG2 gene variants on the pharmacodynamics and pharmacokinetics of ALLO. This effort is a mechanistic genotype to phenotype pharmacogenetic study designed to supplement ongoing investigations of the contribution of genetic variability in drug

transporters to inter-individual variation in drug response. Comparing the variability in uric acid levels and renal clearance of ALLO in individuals with different ABCG2 genotypes will provide information about the extent to which genetic factors contribute to inter-individual differences in the renal elimination and response to ALLO. Investigating these polymorphic variants, which occur at relatively high frequencies within Asians and Europeans, will provide vital information for the purpose of guiding antihyperuricemic drug regimens in these populations.

NUMBER OF SUBJECTS: 15 subjects will participate in the study. 5 from each genotype: homozygous recessive, homozygous dominant, heterozygous. This number has been selected so that our study will be 80% powered to detect a 40% change in allopurinol clearance.

GENDER OF SUBJECTS: Both males and females will be enrolled for this study. Because allopurinol has been shown to have detrimental effects on unborn fetuses, pregnant women will not be allowed to participate in the study.

AGE OF SUBJECTS: Healthy volunteers over 18 years of age will be enrolled

RACIAL AND ETHNIC ORIGIN: Subjects of Asian and European descent will be enrolled in this study. These ethnicities are known to carry the genetic variant of interest for this study.

INCLUSION CRITERIA:

1. Subject self-identify racial background; identify themselves, their parents, and their 4 grandparents as European or Asian;
2. Subjects are generally healthy with approved (normal) laboratory values for:
 - CBC Panel: WBC, RBC, Hemoglobin, Hematocrit, MCV, MCH, MCHC, RDW, Platelet Count, MPV and Differential (Absolute and Percent - Neutrophils, Lymphocytes, Monocytes, Eosinophils, and Basophils)

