 - HFP: Total Protein, Albumin, Globulin (calculated), Albumin/Globulin Ratio (calculated), Total Bilirubin, Direct Bilirubin, Indirect Bilirubin (calculated), Alkaline Phosphatase, AST, ALT
 - RFP: Albumin, BUN/Creatinine Ratio (calculated), Calcium, Carbon Dioxide, Chloride, Creatinine, Estimated Glomerular Filtration Rate (calculated), Glucose, Phosphate (as Phosphorus), Potassium, Sodium, Urea Nitrogen
 - Uric Acid
3. Subjects with the ABCG2 genotype, homozygous, heterozygous or homozygous for the major allele of rs2231142 will be recruited;
4. Subjects >18 years of age and <40 years of age.

EXCLUSION CRITERIA:

1. Patients with vascular disease;
2. Patients with renal impairment (GFR < 60 ml/min);
3. Patients taking medications/supplements that affect uric acid levels;
4. Pregnant or lactating women;

5. Prior history of any allergic reaction to allopurinol/testing positive for HLA-B*5801 allele;
6. Risk of urinary or gastric retention or narrow-angle glaucoma (by medical history examination);
7. Impaired hepatic function (> 1.5 times the upper limit of normal);
8. Evidence of anemia (hemoglobin < 10 g);
9. Evidence or diagnosis of congestive heart failure;
10. Smokers;
11. Subjects with a mutation other than rs2231142 in the ABCG2 genotype;
12. Subjects taking hormonal contraceptives or other hormonal medications;
13. Evidence of recreational drug use as determined by questionnaire;

VULNERABLE SUBJECTS: Students may be enrolled in this study. This study poses little to no risks for healthy students. Only students over 18 will be enrolled and informed consent will be obtained.

METHODS AND PROCEDURES:

Questionnaire:

Effect of the Q141K BCRP variant on the pharmacokinetics and pharmacodynamics of Allopurinol – This questionnaire will be used to assess the subject's inclusion or exclusion from the study. The questionnaire will ask ancestry, health history, medications, habits, and family history. This questionnaire will help determine whether the subject is eligible to participate in the cheek swab portion of the screening.

Procedures, Timeline, and Biological Measures:

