Screening Procedures: Part 1: Once eligible subjects have expressed their interest to participate and have had their questions answered by clinical personnel, the potential subject will be asked to email or call the research staff at Open Medicine Institute, Inc. If the eligible subject is already in the presence of the research staff they may proceed with the visit at the moment. During this visit the research staff will perform a screening evaluation for genotyping to determine eligibility. If email correspondence is preferred a secure network will be used for all correspondence between potential subjects and research staff.

Subjects will be asked to come to Open Medicine Institute, Inc in Mountain View, California, or other site determined by [name], Ph. D (P.I.), to complete a screening visit. The initial screening will include a review of the volunteer's medical history and history of drug use to identify any status that would determine eligibility. If the information on the health, drug use and ethnicity questionnaires are accurate, this will suffice for the inclusion criteria. Changes in medical or drug use history will be noted during the study. The purpose of these questionnaires is to characterize health status and ethnicity as accurately as possible (see Inclusion/Exclusion Criteria). If the volunteer is determined to be eligible to participate after the questionnaire, a cheek swab to determine

the subject's eligibility based on their ABCG2 genotype will be performed.

Part 2: If the genotype group of the subject is not yet full of enrolled subjects, the subject will then be asked to return to Open Medicine Institute, Inc. and an additional venipuncture of 10 ml will be drawn to screen for liver and renal insufficiency within 2 weeks of scheduled study visit. Subject's DNA will also be extracted (either from blood or additional cheek swab) to test for HLA*B 5801 allele, which is associated with allopurinol sensitivity. Female subjects' blood samples will be used for pregnancy testing (see Inclusion/Exclusion Criteria). Remaining saliva or blood sample may be stored for future genome-wide genotyping/sequencing.

The subject may not exercise, drink alcohol, or drink coffee. Strenuous exercise can affect uric acid excretion and alcohol and coffee, both caffeinated and decaffeinated, have been shown to affect uric acid levels.

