Phase I procedures: Subjects will be asked to come to the clinic after 8 hours of fasting to provide a 10 ml blood sample to determine baseline serum uric acid and creatinine concentrations. Female subjects will be asked to provide a urine sample (20 mL) to ensure no change in pregnancy status. Subjects will be asked to empty their bladder and will then be given a placebo (microcrystalline cellulose). Blood samples will be collected at the following time points via an IV catheter: 0.5, 1, 1.5, 2, 3, 4, 5, 6, 8, 10, 24 hours. Subjects will be asked to collect all urine samples during their stay. The volume of the urine will be recorded and 20 ml of the sample stored at -20°C for analysis of uric acid and creatinine content. The remaining urine will then be stored with all other urine samples from the subject until the last time point. Subjects will be asked to return in the morning for their 24 hour blood draw and final urine sample. Subjects will be asked to turn in any urine from overnight. 20 ml of the 24-hour collective urine sample will be stored at -20°C for analysis of uric acid and creatinine.

Phase II Procedures: Day 1: Subjects will be asked to come to the clinic after 8 hours of fasting to provide a 10 ml blood sample to determine baseline serum uric acid and creatinine concentrations. Female subjects will be asked to provide a urine sample (20 mL) to ensure no change in pregnancy status. Subjects will be asked to empty their bladders and will then be given 300 mg of allopurinol. Blood samples collected at the following time points via an IV catheter: 0.5, 1, 1.5, 2, 3, 4, 5, 6, 8, 10, 24 hours. Subjects will be asked to collect all urine samples during their stay. The volume of the urine will be recorded and 20 ml of the sample stored at -20°C for analysis of uric acid, drug, and creatinine content. The remaining urine will then be stored with all other urine samples from the subject until the last time point. Subjects will be asked to return in the morning for their 24 hour blood draw and final urine sample. Subjects will be asked to turn in any urine from overnight. 20 ml of the 24-hour collective urine sample will be stored at -20°C for analysis of uric acid, drug, and creatinine.

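### The visible eligibility criteria exclude hormonal contraceptive users and women already pregnant, but do not require women who could conceive to avoid pregnancy while taking a drug the protocol calls harmful to a fetus

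*Combined protocol and SAP*

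**What the plan says.** Under Gender of Subjects the protocol states the hazard and what follows from it: "Because allopurinol has been shown to have detrimental effects on unborn fetuses, pregnant women will not be allowed to participate in the study". The same paragraph says "Both males and females will be enrolled for this study". Inclusion criterion 4 sets the age range: "Subjects >18 years of age and <40 years of age".

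Two exclusion criteria bear on the point. Item 4 excludes pregnant or lactating women. Item 12 excludes "Subjects taking hormonal contraceptives or other hormonal medications". Protection Against Risks repeats the pregnancy and lactation exclusion as its item 5 and has no item on contraception.

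Pregnancy testing is listed at five points: a blood test at Screening Part 2, and urine tests before placebo, before the Day 1 dose, on Day 2 and before the Day 6 dose. For the placebo day and Day 1 the text gives the purpose: "Female subjects will be asked to provide a urine sample (20 mL) to ensure no change in pregnancy status". The Day 6 test appears in the visit table, not in the Day 6 prose. The Day 7, 8 and 9 rows list no pregnancy test.

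**The concern.** Exclusion 12 removes users of one class of contraception, and the visible criteria ask for nothing in its place. A woman who uses no contraception can therefore meet every written criterion and take six 300 mg doses of a drug that the protocol itself describes as harmful to a fetus.

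The safeguards that are written down look for a pregnancy that already exists. None of them asks the woman to avoid starting one. At stake is a possible fetal exposure in a healthy volunteer, whom the protocol says is unlikely to benefit directly. No estimate, test or power statement is affected.

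**Working it through.** This is mainly a comparison of sections, with some schedule arithmetic.

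**Who may be dosed**

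| Section | What it covers | Does it require avoiding pregnancy? |
|---|---|---|
| Gender of Subjects | States fetal harm; bars pregnant women | No |
| Inclusion criteria, item 4 | Over 18 and under 40 | No |
| Exclusion criteria, item 4 | Women now pregnant or lactating | No |
| Exclusion criteria, item 12 | Users of hormonal contraceptives or other hormonal medication | No |
| Methods and Procedures, with visit table | Pregnancy tests at five points | No |
| Protection Against Risks, item 5 | Women now pregnant or lactating | No |

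Non-hormonal methods are permitted throughout. They are simply not required.

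**Exposure.** Methods and Procedures gives one dose on Day 1, four more on Days 2 to 5, and a final dose on Day 6: 1 + 4 + 1 = 6 doses.

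**Where the last test falls.** The visit table puts the Day 6 visit 120 hours after the first dose. Counting days gives the same figure: (6 − 1) × 24 = 120 hours, or 120 / 24 = 5 days. The final dose follows that test. The last visit, Day 9, is 9 − 1 = 8 days after the first dose.

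**How long a contraception condition would last.** The inputs are the visit-table windows:

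- Screening Part 2 to placebo: up to 2 weeks = 14 days
- Placebo to Day 1: up to 2 weeks = 14 days
- Day 1 to Day 9: 8 days

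The maximum is 14 + 14 + 8 = 36 days. Ending at Day 9 matches the protocol's own sampling for allopurinol and oxypurinol, which runs to about 72 hours after the final dose.

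**What cannot be computed.** The documents give neither the number of women among the 15 subjects nor a conception rate, so no event probability is claimed.

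**The case against.** **The instruction may exist elsewhere.** Subject Comprehension says consent is taken on a form attached to the protocol, and a consent form is a natural place for an instruction to avoid pregnancy. That form (Appendix 1), the questionnaire (Appendix 2), the subject diary (Appendix 3) and the product insert (Appendix 5) are not in the public text. This stands as a limit. A reader might infer that the trial has no contraception requirement at all, and the documents do not support that. The protocol's summary of the questionnaire, "The questionnaire will ask ancestry, health history, medications, habits, and family history", does not mention contraception, but a one-line summary cannot show that the form omits it. What can be said is that the eligibility and risk-protection lists are shown and do not contain the condition.

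**The conduct restrictions prove little.** A reader might draw on the sentence "The subject may not exercise, drink alcohol, or drink coffee" and argue that pregnancy avoidance was considered and left out. The sentence after it explains that these restrictions are there because of effects on uric acid. They control confounding and are not safety rules, so silence on pregnancy there is weak evidence. The point does not rest on it.

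**The test schedule is not a second defect.** A reader might infer that the tests are badly timed, since a Day 6 test would miss any conception on or after the first dose if detection takes more than 5 days. The documents give no detection time. Even granting a longer one, the result follows from a dosing span of only 5 days. The stated purpose of the tests on the placebo day and Day 1 is to confirm that pregnancy status has not changed before dosing, and the schedule serves that purpose. What remains is narrower: testing detects and does not prevent.

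**Exclusion 12 is not an error.** Taken alone it is a reasonable restriction and bars no non-hormonal method. The gap lies in what is not placed beside it.

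**Conclusion.** The point holds for the visible criteria. The protocol names a fetal hazard, admits women of reproductive age, excludes users of hormonal contraception, and in its eligibility and risk-protection lists bars only existing pregnancy or lactation. Following those lists as written would admit a woman at risk of conceiving during the six doses.

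The size is small. With 15 subjects of both sexes and 5 days from first to last dose, the expected number of such events is very low, though the documents do not allow a figure. Sample size, power and analysis are untouched. It is a change worth considering because it concerns participant safety and costs very little.

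The conclusion depends on the protocol's own statement of fetal harm and on no assumption about how fast a pregnancy test turns positive. If the consent form already carries the instruction, what is left is a mismatch between consent form and criteria, which one line would resolve.

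**What to change.** Check the consent form and the other appendices for existing wording. Keep exclusion 12. Add one eligibility criterion, matched to any wording found: women of childbearing potential use effective non-hormonal contraception or abstinence from Screening Part 2 through the last visit. The investigator and the IRB should settle which methods are acceptable.

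The cost is one protocol line and, if the consent form lacks it, one consent line. The condition lasts at most 36 days per woman. No visit, assay, test or analysis changes, and the hormone-free study population is kept. The downside is that a few women may decline to take part.

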Days 2-5: The subjects will receive 4 more doses of allopurinol to be taken once a day until their next visit. Their final inpatient visit must be on Day 6. Adherence will be measured via phone calls and patient diaries. Patients will be asked to keep a log of their

food and drinks.

Day 6: Subjects will be asked to return to the clinic after 8 hours of fasting for their final dose of allopurinol. Subjects will be asked to provide a 10 ml blood sample to determine steady-state levels of drug, creatinine, and uric acid. Subjects will be asked to empty their bladder and they will then be given 300 mg allopurinol. Following their final dose, blood and urine samples will be collected following Phase II: Day 1 procedures. Following the 24-hour time point, subjects will return at least two more times for blood and urine collection up to 72 hours post-allopurinol. **In total, subjects will provide approximately 400 ml of blood.** This is less than a typical blood donation of 500 ml and is below minimal risk of 550 ml for healthy subjects.

| Visit | Timing | Collection |
|--|--|---|
| Screening Part 1 | Anytime | Cheek Swab: ABCG2 genotype Questionnaire |
| Screening Part 2 | Within two weeks of Placebo visit | Blood: CBC, HFP, RFP, UA If female - Pregnancy Cheek Swab: HLA*B 5801 |
| Phase 1: Placebo | Before – Fast 8 hours clinic visit | Blood: Baseline- Creatinine, UA During at 0.5, 1,1.5, 2, 3, 4, 5, 6, 8, 10 hours (Creatinine, UA, ALLO/OXY) Urine: Before – females 20 ml for pregnancy test. During- all urine during stay collected |
| Phase 1: Placebo | 24 hours after placebo dose clinic visit | Blood: Creatinine, UA, ALLO/OXY Urine: Turn in what was collected overnight |
| Phase 2: Allopurinol – Oral 300 mg dose | Before – Fast 8 hours Day 1—clinic visit *Must be started within 2 weeks of Day 0 (Placebo Phase) | Blood: Baseline- Creatinine, UA During at 0.5, 1,1.5, 2, 3, 4, 5, 6, 8, 10 hours (Creatinine, UA, ALLO/OXY_) Urine: Before – females 20 ml for pregnancy test. During- all urine during stay collected |
| Phase 2: Allopurinol – Oral 300 mg tablet | 24 hours after first dose Day 2—clinic visit | Blood: Creatinine, UA, ALLO/OXY Urine: Turn in what was collected overnight – pregnancy test Patient given diaries and tablets to take home for Days 3-6 |
| Phase 2: Allopurinol – Oral 300 mg tablet | 48 hours after first dose Day 3 – at home | Patient Diary and phone follow-ups |

| | | |
|---|---|---|

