| Phase 2: Allopurinol – Oral 300 mg tablet | 72 hours after first dose Day 4 – at home | Patient Diary and phone follow-ups |
| Phase 2: Allopurinol – Oral 300 mg tablet | 96 hours after first dose Day 5 – at home | Patient Diary and phone follow-ups |
| Phase 2: Allopurinol Final Oral 300 mg tablet | 120 hours after first dose Before – Fast 8 hours Day 6 – clinic visit | Blood: Baseline- Creatinine, UA, ALLO/OXY During at 0.5, 1,1.5, 2, 3, 4, 5, 6, 8, 10 hours (Creatinine, UA, ALLO/OXY) Urine: Before – females 20 ml for pregnancy test. During- all urine during stay collected |
| Phase 2: Allopurinol – Follow-up | 24 hours after final dose Day 7 – clinic visit | Blood: Creatinine, UA, ALLO/OXY Urine: Turn in urine that was collected overnight |
| Phase 2: Allopurinol – Follow-up | Day 8 – clinic visit | Blood: Creatinine, UA, ALLO/OXY |
| Phase 2: Allopurinol – Follow-up | As close as possible to 72 hours after injection Day 9 – clinic visit | Blood:, Creatinine, UA, ALLO/OXY |

ANALYTICAL METHODS: Measurement of allopurinol and oxypurinol will be performed by high performance liquid chromatography and mass spectrometry (LC-MS/MS). Measurement of uric acid and its precursors, xanthine and hypoxanthine, will be measured via Amplex Red and Abcam colorimetric assays.

Genotyping: All recruited subjects will sign informed consents and HIPAA forms. At screening, a blood sample (10 mL) or saliva sample will be obtained for DNA extraction. Plasma will be stored for assays of endogenous compounds and drugs. The ABCG2 variants will be genotyped at UCSF by a Taq Man Assay using primers and probes from ABI. The reaction will be run on an ABI 7900 HT.

HLA genotyping and wellness panels will be analyzed by qualified personnel at OMI or other reputable company as approved by [name] or other study personnel.

STATISTICAL ANALYSIS:

Mechanistic pharmacokinetic modeling will be conducted to characterize the pharmacokinetics of allopurinol (ALLO) and oxypurinol (OXY). The mechanistic model will characterize details relevant for this study such as conversion mechanism from ALLO to OXY and estimation of fraction of metabolized drug; estimation of ALLO and OXY renal and secretory clearance; possible concentration-dependent saturation

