mechanism of secretory clearance and consequent longitudinal changes in OXY secretory CL and influence of pharmacogenomics (ABCG2) and demographic covariates (creatinine clearance, age, gender, race and body weight) on secretory and renal CL. By use of the physiological model, we will also attempt to estimate the drug concentration in the renal tubule; by knowing plasma and urinary concentration of OXY, and by estimating filtration and secretory clearance of OXY, we will be able to estimate the time profile of tubular concentrations of OXY. These tubular OXY concentrations represent concentration at the proposed site of action and they will further be linked with the pharmacodynamic response. A model describing concentration dependent inhibition of UA re-absorption from the renal tubule by OXY will be implemented. We will examine linear and non-linear (Emax type of model) relationships between tubular OXY and inhibition of UA reabsorption. In the pharmacokinetic modeling, we expect to see a significant influence of creatinine clearance on renal clearance and a significant influence of ABCG2 genotype on secretory CL and oral bioavailability, as described below. In the pharmacokinetic-pharmacodynamic analysis we expect that individuals with higher tubular concentrations of OXY will show the better response in terms of plasma UA lowering resulting in higher urine UA concentrations. Consequently, higher tubular concentrations will be mostly expected in individuals with high secretory clearance, e.g. individuals with ABCG2 141Q/Q, however the modeling may also account for other factors contributing to high tubular concentration, such as higher filtration rates and other factors, therefore providing more granularity and better mechanistic understanding in all processes leading to overall UA physiology. Although this specific PKPD analysis will be focused on the mechanism and role of ABCG2 in UA response to ALLO and OXY, the established mechanistic framework can be used to test the role of potential new pharmacogenetic variants. Longitudinal PKPD modeling using nonlinear mixed effects is a method carrying the most power to separate the signal from the noise; therefore modeling analysis will be associated with at least 80% power to detect differences in primary endpoints (net secretory clearance and change in UA) as described above. In addition to confirming the result of the primary analysis, this analysis will establish a mechanistic representation of the physiology underlying UA metabolism, therefore providing strong support and evidence to our mechanistic hypothesis. Pharmacokinetic parameters including renal clearance, and net reabsorptive or secretory clearance of UA, OXY and ALLO will be calculated from serum and plasma drug levels by standard pharmacokinetic methods. To assess net secretory or reabsorptive clearance of the three compounds, we will subtract $f_u \cdot \text{GFR}$ (where f_u is the unbound fraction of ALLO, OXY or UA and GFR is the glomerular filtration rate), as measured or estimated from serum and urine creatinine values, from renal clearance of ALLO, OXY and UA, directly measured from plasma and urine values. Previously we have used these methods to calculate net secretion (or reabsorption) of several drugs. For pharmacodynamics, differences in DSUA between the genotype groups will be evaluated first with an analysis of variance. If DSUA is not normally distributed, we will evaluate the differences between the genotype groups using a non-parametric Kruskal-Wallis test. We expect individuals with ABCG2 141K/K and 141Q/K will have a reduced response to ALLO (smaller DSUA) than individuals with ABCG2 141Q/Q. In addition, individuals with ABCG2 141K/K will have reduced renal clearance of ALLO and OXY in comparison to other genotypes since we propose that ABCG2 functions as a secretory

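### The Day 2 row labels take-home tablets for Day 6, a day on which the plan gives the dose in clinic after a pre-dose sample

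*Combined protocol and SAP*

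**What the plan says.** The Day 2 row of the visit table (Methods and Procedures) is a clinic visit 24 hours after the first dose. Its collection cell ends: "Patient given diaries and tablets to take home for Days 3-6". The next three rows, for Days 3, 4 and 5, are marked as home days with diary and phone contact.

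The Day 6 row, headed "Phase 2: Allopurinol Final Oral 300 mg tablet", is a fasted clinic visit with a baseline sample that includes ALLO/OXY. The Day 6 text sets the order of events. The subject comes in fasted for the last dose and first has blood drawn, which the text describes as follows: "Subjects will be asked to provide a 10 ml blood sample to determine steady-state levels of drug, creatinine, and uric acid". Dosing comes only after that draw, and the text places it in the clinic.

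For the days between, the Days 2-5 text says: "The subjects will receive 4 more doses of allopurinol to be taken once a day until their next visit". It then fixes that visit on Day 6.

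**The concern.** The dispensing line covers a day on which, by every other statement in the plan, the subject should arrive without having dosed. It is the only instruction shown that says which days the home supply is for. No sentence says that the clinic holds the Day 6 tablet, or that the subject must not dose at home that morning.

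The Day 6 pre-dose draw is the only sample that the text calls steady-state. The Statistical Analysis section names as "primary endpoints (net secretory clearance and change in UA" two quantities that draw on these data, and it plans longitudinal PK/PD modelling, for which dose history is an input. A tablet at home on Day 6 would turn the pre-dose sample into a post-dose one and put an extra dose under the profile. For women it would also precede the Day 6 urine check ("females 20 ml for pregnancy test"), which the row lists under the before-visit items.

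**Working it through.** This is a count of doses by day and setting; no sample-size or power formula is involved.

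**1. The plan's own dose count.** Text: Day 1 (1) + Days 2-5 (4) + Day 6 (1) = 6. Table rows labelled 300 mg, at 0, 24, 48, 72, 96 and 120 hours: 6. Text and table agree.

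**2. Home days against dispensed days.**

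| Day | Setting in the table | In the Day 2 take-home range? |
|---|---|---|
| 1 | Clinic | No |
| 2 | Clinic (where the tablet is taken is not stated) | No |
| 3 | Home | Yes |
| 4 | Home | Yes |
| 5 | Home | Yes |
| 6 | Clinic, fasted, dose after sample and voiding | Yes |

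Home days: 3. Days in the dispensing range: 4. The excess day is Day 6.

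**3. Is there a surplus tablet?** The cell gives no tablet count, so there are two cases.

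- *Day 2 tablet taken in clinic.* The home supply should cover Days 3-5, so 3 tablets. A supply for Days 3-6 is 4, a surplus of 1.
- *Day 2 tablet taken from the supply.* The supply should cover Days 2-5, so 4 tablets. Four is then the right number with the wrong day labels, and no tablet is left for a home dose on Day 6.

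**4. Every line followed literally.** Day 1 in clinic (1) + Day 2 outside the take-home range (1) + Days 3-6 at home (4) + Day 6 in clinic (1) = 7 tablets, against 6 planned. Day 6 intake is 2 × 300 = 600 mg. The blood sample meant to follow 5 doses (Days 1-5) follows 6.

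**5. After correction.** Day 1 (1) + Day 2 (1) + Days 3-5 at home (3) + Day 6 in clinic (1) = 6, which agrees with the text and with every row.

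**The case against.** The best defence is that the intent is plain. Home dosing runs until a visit fixed on Day 6, and both the Day 6 text and row put the final dose in clinic after the sample. Harm requires someone to let one day range override several explicit statements. The range also governs diaries and tablets jointly, and Days 3-6 may be right for the diaries. The consent form and diary (Appendices 1 and 3) are not shown and may instruct subjects correctly. All of this stands, and it limits the likelihood of harm. It does not make the tablet label right. A further suggestion, that the subject carries the Day 6 tablet to the clinic, is stated nowhere.

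A reader might infer several stronger things that the documents do not support:

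- *The dose clock is wrong for all 14 blood samples from Day 6 on (1 pre-dose + 10 + 1 at 24 hours + 2 on Days 8 and 9), and early urine is lost.* This needs the clinic to give no tablet, which contradicts the Day 6 text. With the clinic tablet given, time since the latest dose is correct for the 13 post-dose samples. Any size for the shift would also need a lead time that the documents do not give.
- *The subject is overdosed.* 600 mg lies within the 100 to 800 mg daily range under Potential Risks.
- *A primary endpoint fails.* An extra dose raises both urinary excretion and plasma exposure over the same interval, and no effect on net secretory clearance has been shown. For change in uric acid, the Statistical Analysis section does not say which sample defines it, so no effect can be sized.
- *Only Days 3-5 can be home-dosing days.* That is the table's labelling, but the plan does not settle where the Day 2 tablet is taken.

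**Conclusion.** The point holds as an inconsistency in a current dosing instruction: the take-home tablets carry a Day 6 label that the rest of the plan contradicts. That conclusion rests on the wording alone and is firm.

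The consequence is conditional. It assumes that the Day 2 tablet does not come from the supply, that the subject follows the label, and that the clinic also doses as written. Then, per affected subject, there is one extra 300 mg tablet, one steady-state sample that is no longer pre-dose, and a Day 6 profile after two doses. The documents do not say how many subjects this could touch; with 5 per genotype, one subject is 1/5 = 20% of a group. Day 1 data, sample size and power do not change. Because the Day 6 text shows the intent, the risk is limited, but the line should be corrected because staff would dispense from it.

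**What to change.** - In the Day 2 row, write: *diaries for Days 3-6 and tablets for Days 3-5*, and state that the Day 2 tablet is given at that visit, so 3 tablets go home. If the sponsor intends Day 2 to be taken at home, write *tablets for Days 2-5* and dispense 4.
- In the Day 6 text, add that no tablet is taken at home that day and that the clinic gives the dose only after the pre-dose sample and voiding.

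The cost is one day range and about two sentences. No visit, procedure or sample is added. Check the diary and consent form for the same range when the change is made.
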